## LIST OF ABBREVIATIONS/DEFINITIONS

AE	Adverse event
ALT	Alanine transaminase/SGPT
Allograft	Transplant from one person to another person
AST	Aspartate transaminase/SGOT
Autograft	Transplant from one anatomical location to another within the same person
BSA	Bovine serum albumin
BSE	Bovine spongiform encephalopathy
CBC	Complete blood count
CBER	Center for Biologics Evaluation and Research
CFR	Code of Federal Regulations
CMF	Comprehensive metabolic panel
CRF	Case report form
CRO	Contract research organization
DoD	Department of Defense
DSMB	Data and safety monitoring board
FDA	Food and Drug Administration
FPRS	Wong-Baker FACES pain rating scale
GCP	Good clinical practice
HgB	Hemoglobin
HIPAA	Health Insurance Portability and Accountability Act
HRPO	Human Research Protection Office
IB	Investigator's brochure
ICH	International Conference on Harmonisation
IND	Investigational new drug
IRB	Institutional review board
MHC	Major histocompatibility complex
MM	Medical monitor
NIKS®	Near-diploid human keratinocytes
ORP	Office of Research Protections
PHI	Protected health information
POSAS	Patient and observer scar assessment scale
PRA	Panel reactive antibodies
QA	Quality assurance
QC	Quality control
SAE	Serious adverse event
SD	Standard deviation
SOC	Standard of care
TBSA	Total body surface area
UPIRTSO	Unanticipated problem involving risks to subjects or others
USAMRMC	U. S. Army Medical Research and Materiel Command
WBC	White blood cells

## SUMMARY OF STRATA2014 PROTOCOL

### TITLE OF STUDY

Open-label, controlled, randomized, multicenter, dose escalation study evaluating the safety, tolerability, and efficacy of single or multiple applications of StrataGraft® skin tissue as an alternative to autografting full-thickness complex skin defects

### CLINICAL PHASE

Phase II

### STUDY OBJECTIVE

The objective of this study is to assess the safety, tolerability, and efficacy of increasing dosages of a single or multiple applications of StrataGraft skin tissue in the treatment of full-thickness complex skin defects on the arms, legs, and torso.

### STUDY RATIONALE

The current standard of care (SOC) for severe burns and other complex skin defects is surgical harvesting of a sheet of healthy skin from an uninjured site on the patient and transplantation of this autologous skin graft to the wound after excision of non-viable tissue. While this process can be effective in providing closure of the original wound, it has significant limitations related to the iatrogenic donor site wounds created during surgical removal of autologous skin tissue. These donor site wounds are extremely painful, prone to infection and scarring, and can themselves convert to full-thickness wounds that must then be managed to promote healing. In addition, the amount of healthy skin available for harvesting is frequently limited in large burns, necessitating sequential re-harvesting of available donor sites. As a result, there is an urgent need for alternatives to donor site harvesting for treatment of severe burns and other complex skin defects.

This range-finding study is designed to evaluate StrataGraft skin tissue as an alternative to autografting in promoting autologous tissue regeneration of the full-thickness component of complex skin defects resulting from acute traumatic skin loss (e.g., burn or degloving injuries). StrataGraft skin tissue is an off-the-shelf, biologically active human skin substitute which is anticipated to provide immediate wound coverage and aid in wound bed conditioning and tissue regeneration. Based on over 25 years of clinical experience with human skin substitutes containing living allogeneic cells, as well as prior clinical experience with StrataGraft skin tissue, it is anticipated that StrataGraft skin tissue will remain in the wound long enough to promote autologous tissue regeneration and be replaced over time by the subject's own cells rather than permanently engrafting.

Stratatech has completed STRATA2001, a first-in-human, dose escalation trial evaluating the safety of StrataGraft skin tissue in subjects with complex skin defects of 5-73% total body surface area (TBSA) resulting from thermal injury, trauma, or necrotizing fasciitis. This study showed that autograft take in wound beds temporized with StrataGraft skin tissue was comparable to autograft take in wounds temporized with cadaver allograft. No product-related adverse events (AE) were seen following application of StrataGraft skin tissue to the full-thickness component of these complex skin defects for seven days. There was no change in the types of AE as the total

---

dosage of StrataGraft skin tissue increased 5-fold across the three cohorts from 44 cm^2 to 220 cm^2. StrataGraft skin tissue remained intact and viable throughout the seven day placement period, suggesting the potential for continued biological activity during longer exposure.

The STRATA2011 study, a follow-up to the STRATA2001 trial, has been conducted as an open-label, dose-escalation, multicenter study evaluating the safety, tolerability, and efficacy of prolonged exposure to increasing dosages of a single application of StrataGraft skin tissue in promoting the healing of complex skin defects with intact dermal elements. In STRATA2011, a single application of StrataGraft tissue was applied to the deep partial-thickness portion of thermal burns and left in place to evaluate whether StrataGraft could promote autologous tissue regeneration thereby reducing or eliminating the need for the surgical harvesting of a donor site for autografting.

The STRATA2011 study included subjects with complex skin defects whose total injury areas range from 3-43% TBSA due to thermal injury. Each subject had two comparable wound areas containing intact dermal elements that were identified and randomized to receive StrataGraft or an autologous skin graft. Thirty subjects were enrolled in this dose escalation study and those in cohort 1 received up to 220 cm^2 while those in cohorts 2 and 3 received up to 440 cm^2 of StrataGraft skin tissue. None of the study sites treated with StrataGraft skin tissue required autografting by day 28 (primary efficacy endpoint). No safety signal was seen following application of StrataGraft skin tissue, and 27 of the 28 per-protocol subjects had complete wound closure of treatment sites at the 3 month study session (primary safety endpoint). The presence of DNA from StrataGraft tissue was assessed after three months to evaluate whether StrataGraft tissue had permanently engrafted. Molecular analysis of patient biopsy samples found no evidence of DNA from cells of StrataGraft tissue.

The STRATA2001 and STRATA2011 studies provided several important clinical findings that have informed the development of this phase II STRATA2014 protocol:

- StrataGraft remains intact, adherent, and viable in complex skin defects for at least seven days, during which time it is anticipated to act as a continuous source of factors that are involved in promotion of autologous tissue regeneration.
- StrataGraft tissue does not permanently engraft and is replaced by the patient's own cells by three months.
- None of the complex skin defects containing intact dermal elements treated with StrataGraft tissue required autografting by day 28 eliminating the need for autografting. These results exceeded the expectations established prior to the study that a 50% reduction in the StrataGraft-treated area that ultimately requires autografting would be clinically meaningful.
- The absence of donor site harvest for areas treated with StrataGraft tissue resulted in significantly less pain and other morbidities as well as improved cosmesis associated with the prospective donor site wounds.

The STRATA2014 study builds upon the data generated in the STRATA2001 and STRATA2011 studies in the same patient population as that for STRATA2001. The proposed study is designed as an open-label, controlled, randomized, multicenter, dose-escalation study evaluating the safety, tolerability, and efficacy of single or multiple applications of StrataGraft skin tissue as an

alternative to donor site harvesting and autografting in promoting the healing of full-thickness complex skin defects. The proposed study population will include subjects with up to 49% TBSA complex skin defects including a full-thickness component. Targeted enrollment for this study is up to 20 subjects with full-thickness complex skin defects requiring surgical excision and autografting. Subjects will be sequentially enrolled in two cohorts of increasing dosage of StrataGraft skin tissue (treatment area per surgical application). Subjects will be eligible to receive up to three applications of StrataGraft skin tissue in the treatment of full-thickness skin defects. In the first cohort, up to 10 subjects will receive an initial surgical application of up to 200 cm^2 of StrataGraft skin tissue. The second cohort will enroll up to 10 subjects who will receive an initial treatment of up to 400 cm^2 of StrataGraft skin tissue. The treatment site will be evaluated to assess the progress of wound healing. Per the clinical judgment of the Clinical Investigator and as necessary to promote complete wound closure, wounds may be treated with up to two additional applications StrataGraft tissue. The cumulative study dosage for cohort 1 may be up to 600 cm^2 and for cohort 2 may be up to 1200 cm^2.

Two comparable wounds in each subject will be identified and the wounds randomized to receive StrataGraft skin tissue or a surgically harvested autologous skin graft. The inpatient comparator design allows for a matched control to eliminate significant underlying immunologic, physiologic, and scarring variables inherent in this population. Two donor sites will be prospectively designated to provide a source of autograft skin for the control treatment site and, if needed, the StrataGraft treatment site. Both the StrataGraft skin tissue and autograft control will be placed on the treatment sites immediately following surgical excision of non-viable tissue. After the fifth subject in cohort 1 reaches the three month study session, an interim safety report will be generated and reviewed by the Data and Safety Monitoring Board (DSMB). Progression to cohort 2 will take place only after a favorable review of the safety information by the DSMB.

Efficacy will be assessed by evaluating the percent area of the StrataGraft treatment site requiring autografting by 3 months, pain of the donor sites through day 28, and the incidence of complete wound closure at three months supported by clinical photography. Cosmesis of the treatment sites will be evaluated at 3, 6, and 12 months. Additional assessments will include persistence of allogeneic DNA in the StrataGraft-treated sites as well as cosmesis and pain of the donor sites. Safety assessments will include monitoring of AE, vital signs, laboratory safety values, incidence of wound infection, and immunologic responses to StrataGraft tissue.

In addition to routine safety monitoring by the study's medical monitor (MM) and the DSMB, the study will have a Department of Defense (DoD) research monitor whose sole responsibility will be to assess safety. The decision to advance to cohort 2 will be based on an interim safety analysis by the DSMB after the fifth subject in the first cohort has completed the 3 month visit. This time frame will allow for the evaluation of acute, sub-acute, and early chronic AE resulting from prolonged exposure and multiple applications of StrataGraft skin tissue in these subjects. Enrollment into the second cohort will begin only after the DSMB has reviewed the interim safety data and recommended progression. A copy of the interim analysis will also be submitted to the Investigational New Drug (IND) on file for StrataGraft skin tissue.

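### Do cohorts defined only by area ceilings (200 and 400 cm²) undermine the assessment of increasing dosage?

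*Combined protocol and SAP*

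**What the plan says.** The Study objective is "to assess the safety, tolerability, and efficacy of increasing dosages of a single or multiple applications of StrataGraft skin tissue", and the Study rationale adds: "This range-finding study is designed to evaluate StrataGraft skin tissue as an alternative to autografting". The same section defines the cohorts: "Subjects will be sequentially enrolled in two cohorts of increasing dosage of StrataGraft skin tissue (treatment area per surgical application"). The two levels are then given as maxima: "In the first cohort, up to 10 subjects will receive an initial surgical application of up to 200" cm², and "The second cohort will enroll up to 10 subjects who will receive an initial treatment of up to 400" cm². The site-specific inclusion criteria and the dose regimen section repeat these limits, again as maxima.

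Up to three applications are allowed. On total area, "The cumulative study dosage for cohort 1 may be up to 600" cm²; the limit for cohort 2 is 1200 cm².

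Entry to cohort 2 follows enrolment order and a safety gate: "Progression to cohort 2 will take place only after a favorable review of the safety information by the DSMB". Randomization acts within the subject, with "the wounds randomized to receive StrataGraft skin tissue or a surgically harvested autologous skin graft".

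The Statistical methods section of the synopsis names only routine statistical measures and the SAS package.

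**The concern.** A dose-escalation study normally lets the reader equate cohort with dose. Here the whole permitted range of cohort 1 lies inside that of cohort 2. A subject treated with 200 cm² or less complies with either cohort, and the number of cohort 2 subjects above 200 cm² could be anything from 0 to 10. If results were reported by cohort alone, similar findings in the two cohorts might mean only that similar areas had been treated. A statement about the safety of more than 200 cm² per application might then rest on far fewer subjects than the cohort size suggests.

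Cumulative exposure is not ordered by cohort either. A cohort 1 subject with three full applications may receive more in total than a cohort 2 subject with one.

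**Working it through.** **Inputs.** Ceilings of 200 and 400 cm², at most three applications, cumulative limits of 600 and 1200 cm², and up to 10 subjects per cohort, all from the Study rationale. The share of cohort 2 subjects above 200 cm² is not in the documents and is an assumption throughout.

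**1. The plan's own figures.** Applications × ceiling: 3 × 200 = 600 cm² and 3 × 400 = 1200 cm². Both match, which supports reading the ceilings as applying to each application, although the numeric limits are attached to the initial one.

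**2. Overlap.** Permitted area per application is above 0 and up to 200 cm² in cohort 1, and above 0 and up to 400 cm² in cohort 2. The first range is contained in the second. For cumulative area, 600 cm² (cohort 1, three applications) exceeds 400 cm² (cohort 2, one application). This does not conflict with the plan, which defines cohort dosage per application and nowhere says that cohorts order cumulative exposure.

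**3. How many cohort 2 subjects might exceed 200 cm².** Take the number as Binomial(10, p), with p assumed. Then the mean is 10p and P(none) = (1 − p)^10.

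| Assumed p | Expected number | P(none) | P(5 or fewer) |
|---|---|---|---|
| 0.10 | 1.0 | 0.349 | 0.9999 |
| 0.25 | 2.5 | 0.056 | 0.980 |
| 0.50 | 5.0 | 0.001 | 0.623 |
| 0.75 | 7.5 | <0.001 | 0.078 |
| 0.875 | 8.75 | <0.001 | 0.0045 |

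**4. Effect on a safety statement.** With zero events in n subjects, the two-sided 95% Clopper-Pearson upper limit is 1 − 0.025^(1/n).

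| n above 200 cm² | Upper limit |
|---|---|
| 10 | 30.8% |
| 9 | 33.6% |
| 5 | 52.2% |
| 3 | 70.8% |
| 1 | 97.5% |

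The loss relative to a full cohort runs from about 3 percentage points (33.6 − 30.8 = 2.8) to about 67 (97.5 − 30.8 = 66.7). Nothing in the documents says where in that range the trial will fall.

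**5. What in the synopsis depends on cohort as a measure of dose.**
- Primary endpoints: one is a percentage of the treated site, so it is already scaled to area; the other is wound closure. Neither is defined by cohort.
- Comparison with autograft: made within the subject between two sites of comparable depth and area, so cohort cancels out.
- Escalation gate: reviews cohort 1 subjects before cohort 2 opens, so overlap arising in cohort 2 cannot alter it.
- Between-cohort or dose-response test: none is stated.

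No stated rule or number gives a wrong result because of the overlap.

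**The case for a change.** The best argument for acting is that the objective speaks of increasing dosages and the rationale calls the study range-finding, while nothing in the synopsis pushes treated area upward. Eligibility works the other way: it needs two comparable sites, each a single contiguous full-thickness wound away from joints and other excluded regions, with donor skin held in reserve. The preceding study is also described only by its ceilings (220 and 440 cm²), so a reader cannot tell how many of its subjects exceeded the lower one. A clarifying sentence and a few descriptive tables would cost little.

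Part of this stands. Cohort is not a measure of area received, and a report that treated it as one would overstate its evidence. The rest does not amount to a fault in the plan:
- The harm arises only if results are shown by cohort alone and a higher-dose claim is built on them. The synopsis proposes neither.
- The clarification is already there, since every statement of cohort area is worded as a maximum.
- Tables of area applied belong in an SAP or table shells. Their absence from a synopsis is not evidence that they are missing.
- Such tables would be observational: area follows wound size, the cohorts are sequential, and re-application is at the investigator's discretion. With at most 20 subjects they would not establish a dose-response.
- The cost is less certain for cumulative area, because the synopsis does not say that area is recorded at each re-application.

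**Conclusion.** The observation is correct and no change to the plan follows. The cohorts are ceilings on area, so cohort 2 membership does not show that a subject received more than 200 cm² per application. The gated raising of the ceiling, the primary endpoints and the within-subject comparison are unaffected.

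What is left is reporting detail that an analyst would normally supply: the initial area actually applied, the number of cohort 2 subjects above 200 cm², and any remark about the larger area confined to those subjects. The consequence of leaving that out could be trivial (upper limit 34% against 31%) or large (97.5% against 31%). Those figures assume zero events, a full cohort of 10 (itself a maximum) and shares that the documents do not supply. The conclusion rests on the synopsis; the full protocol or SAP may already set a minimum area or plan an exposure table. No view is taken on what area should be applied.

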## **STUDY DESIGN**

### **Primary clinical endpoints**

- Percent area of the StrataGraft treatment site requiring autografting by 3 months
- Wound closure of the treatment sites at 3 months

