### Secondary clinical efficacy assessments

- Percent of subjects requiring autografting of the StrataGraft treatment site by 3 months
- Incidence of complete wound closure of the treatment sites at 3, 6, and 12 months
- Percent wound closure at 3, 6, and 12 months
- Cosmesis of treatment sites at 3, 6, and 12 months
- Cosmesis of donor sites at 3, 6, and 12 months
- Pain of donor sites measured at days 3, 7, 14, 21, and 28

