### Study Assessments (efficacy)

Assessments	Methods	Schedule of Assessments
Percent area of treatment site requiring autografting	Clinician assessment supported by photodocumentation	Days 3, 7, 14, 21, 28 and 3 months
Wound closure of treatment sites	Clinician assessment supported by photodocumentation	3, 6, and 12 months
Cosmesis of treatment sites	POSAS supported by photodocumentation	3, 6, and 12 months
Cosmesis of donor sites	POSAS supported by photodocumentation	3, 6, and 12 months
Pain of donor sites	Wong-Baker FACES pain rating scale (FPRS)	Days 3, 7, 14, 21, and 28

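### No efficacy endpoint or scheduled assessment counts autografting of the StrataGraft site after 3 months, although closure and cosmesis of that site are scored to 12 months

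*Combined protocol and SAP*

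**What the plan says.** The places cited are all in the protocol summary of the combined protocol and SAP.

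- **Autografting.** The first primary endpoint is "Percent area of the StrataGraft treatment site requiring autografting by 3 months". Its secondary companion is "Percent of subjects requiring autografting of the StrataGraft treatment site by 3 months". In the efficacy table under Study Assessments, the autografting row is scheduled for "Days 3, 7, 14, 21, 28 and 3 months" and ends there.
- **Closure.** The second primary endpoint is "Wound closure of the treatment sites at 3 months". The secondary list adds "Incidence of complete wound closure of the treatment sites at 3, 6, and 12 months" and "Percent wound closure at 3, 6, and 12 months".
- **Cosmesis.** The secondary list has "Cosmesis of treatment sites at 3, 6, and 12 months", rated by POSAS, and the same time points for the donor sites.
- **Follow-up.** Each subject is followed for 12 months.
- **Availability of autograft.** The Study Rationale and the inclusion criteria reserve a donor site in case the StrataGraft site needs autografting. Neither gives a date after which it may no longer be used.
- **Expected course.** The Study Rationale reports from the two previous studies that "StrataGraft tissue does not permanently engraft and is replaced by the patient's own cells by three months".
- **Analysis.** The Statistical methods entry names standard measures and SAS. It has no rule for a StrataGraft site that was autografted before a closure or cosmesis assessment.

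**The concern.** The trial asks whether StrataGraft can replace donor-site harvest and autografting in full-thickness wounds. Autografting of the StrataGraft site is therefore the failure event of interest, yet its count stops 9 months before follow-up ends.

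Take a site that is closed at 3 months, breaks down, and is autografted in month 4. It adds nothing to either autografting endpoint. If the graft takes, the site scores as closed at 6 and 12 months, under the StrataGraft label. Its POSAS ratings then describe, in whole or in part, autografted skin, so that for this subject the within-patient comparison sets autograft against autograft.

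The earlier studies, as summarised, do not allow late autografts to be assumed absent. The first-in-human study left the product on full-thickness wounds for seven days and then assessed autograft take. The second study treated deep partial-thickness burns with intact dermal elements. Neither describes long-term closure of full-thickness wounds without autograft.

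At stake is what the 6- and 12-month results can be said to show. No stated decision depends on them: progression to cohort 2 rests on a safety review.

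**Working it through.** The plan states no figure that depends on this point, so there is nothing to reproduce. The check compares the endpoint windows and then works out what one late autograft is worth.

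**1. Windows for the StrataGraft site**

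| Item | Last time point | Condition on earlier autografting |
|---|---|---|
| Area autografted (primary) | 3 months | it is the event itself |
| Share of subjects autografted (secondary) | 3 months | it is the event itself |
| Scheduled autografting assessment | 3 months | it is the event itself |
| Complete closure, percent closure | 12 months | none stated |
| Treatment-site cosmesis | 12 months | none stated |

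Scored follow-up without an autografting count: 12 − 3 = 9 months.

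**2. Which late autografts escape**

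- Site open at 3 months and judged then to need grafting: it can count in the autografting endpoints, because they are worded in terms of need, and it counts as not closed at 3 months.
- Site open at 3 months, not judged to need grafting, grafted later: not in the autografting endpoints, but not closed at 3 months.
- Site closed at 3 months that breaks down and is then grafted: a success on every 3-month endpoint.

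Once grafted and healed, all three can score as closed at 6 and 12 months.

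**3. Value of one site.** Planned enrolment is up to 20, in two cohorts of up to 10. One subject is 1/20 = 5 percentage points overall and 1/10 = 10 points within a cohort.

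**4. Illustration.** Assume that all N StrataGraft sites are closed at 12 months and that k of them closed only after an autograft later than 3 months. Both the full closure and the values of k are assumptions. As written, closure is N/N = 100% whatever k is. Closure without late autograft is (N − k)/N, shown with exact (Clopper-Pearson) 95% intervals:

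| k | N = 20 | N = 10 |
|---|---|---|
| 1 | 95% (75.1 to 99.9) | 90% (55.5 to 99.7) |
| 2 | 90% (68.3 to 98.8) | 80% (44.4 to 97.5) |
| 3 | 85% (62.1 to 96.8) | 70% (34.8 to 93.3) |

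**5. Chance that the issue arises at all.** For an assumed per-subject risk p of a late autograft, independent between subjects, P(at least one) = 1 − (1 − p)^N:

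| p | N = 20 | N = 10 |
|---|---|---|
| 5% | 64% | 40% |
| 10% | 88% | 65% |
| 20% | 99% | 89% |

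**The case against.** The strongest reply is that this affects little that matters. Three months is a reasonable primary time point, and the reported replacement of the product by the subject's own cells by then can be read as support for it. No primary result changes. The affected results are secondary, in an open-label phase II study of up to 20 subjects, with no stated hypothesis test attached. Most sites grafted soon after 3 months would have been open at 3 months, and so already count as failures of the closure primary. All of this stands, and it limits the point to the 6- and 12-month results.

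A reader might go further and infer that late autografts would be recorded nowhere. The documents do not support that. Adverse events are collected throughout, closure and cosmesis are photographed, and late harvest of the reserved donor site could show in donor-site cosmesis. But autografting is not named as an adverse event, and none of these sources yields a count or an area, or changes how the site is scored.

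A reader might also call a 3-month autograft-free rate overstated if the 12-month rate would be lower. That compares two time points; a 3-month figure labelled as such misstates nothing.

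It can also be said that the missing scoring rule applies equally to autografts before 3 months. That is true, but those are at least counted in the autografting endpoints. Finally, the text cited is a protocol summary. If the full protocol or SAP records later autografts and says how they are scored, only the summary needs aligning.

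**Conclusion.** The point holds for the 6- and 12-month results and should be corrected. The plan follows the StrataGraft site for 12 months but counts its autografting for only 3. The later closure and POSAS results can therefore credit autografted sites to StrataGraft, and the trial cannot report how many subjects remained free of autograft at that site for a year.

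It does not follow that the 3-month endpoints are biased; autografts done later cannot alter them.

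The size is 5 points per late-autografted site at N = 20, or 10 points at N = 10, provided that full enrolment is reached and the site closes after grafting. How many such sites there would be is unknown. The values of k and p in the working are assumptions that show the range; they are not estimates.

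**What to change.** 1. Keep both 3-month primary endpoints as they are.
2. In the efficacy table under Study Assessments, add 6 and 12 months to the autografting row.
3. Under Secondary clinical efficacy assessments, add the cumulative percent area of the StrataGraft site autografted, and the percent of subjects with any autografting of that site, each by 6 and by 12 months.
4. State in the analysis that closure and cosmesis of the StrataGraft site at 6 and 12 months will be reported in two ways: regardless of autografting, and with sites autografted at any earlier time shown as a separate category.

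The cost is one added item at two visits that already take place, two added secondary endpoints, and one extra breakdown in the tables. No visit, procedure or rule of clinical management changes. The sponsor also accepts that the long-term figure may look less favourable than the 3-month one.
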